#### 7.2.4.1.3 Assessment of mechanisms of resistance to PDR001

Mechanisms of resistance to PDR001 will be explored with pretreatment, on-treatment and disease progression tumor samples (archival tumor samples and/or newly collected tumor biopsy samples, as appropriate). Optimal sample collection for the study of resistance will include a newly obtained tumor biopsy taken at screening if not collected at molecular pre-screening, a biopsy taken during therapy (approximately start of cycle 3, alternative times are likely to be acceptable after discussion with Novartis), and a biopsy taken at the time of disease progression / resistance, ideally from a growing lesion if it is safe and feasible for the patient. If a patient has not provided an on therapy tumor sample, they may still be considered for a biopsy at resistance. Duplicate samples will not be collected: specifically, any baseline and on therapy biopsies provided for pharmacodynamic assessments will meet the needs of studying resistance to treatment. The sample at time of disease progression should be collected only from patients who have had a response to treatment as defined by the investigator. This may include a notable period of stable disease and need not require a RECIST or irRC-defined response. The tumor sample at progression of disease should be obtained within 28 days after the last dose of study treatment and no more than 14 days after starting a new antineoplastic therapy. If a patient has progressive disease as best response to treatment, then the biopsy at time of progression of disease should not be collected.

The sample collection information must be entered on the appropriate CRF page(s).

[REDACTED]

[REDACTED]

[REDACTED]

[REDACTED]

[REDACTED]

[REDACTED]

[REDACTED]

## Other assessments

No additional tests will be performed on patients entered into this study.

## 8 Safety monitoring and reporting

### 8.1 Adverse events

#### 8.1.1 Definitions and reporting

An adverse event is defined as the appearance of (or worsening of any pre-existing) undesirable sign(s), symptom(s), or medical condition(s) that occur after patient's signed informed consent has been obtained.

For patients with unknown molecular status and who sign the molecular pre-screening ICF, AEs which occur after signature of this consent will only be captured if they meet the definition of serious as outlined in [Section 8.2](#) and are reported to be causally related with study procedures (e.g. an invasive procedure such as biopsy). Once the main study ICF is signed, all AEs per the descriptions below will be captured in the Adverse Event CRF.

Abnormal laboratory values or test results occurring after informed consent constitute adverse events only if they induce clinical signs or symptoms, are considered clinically significant, require therapy (e.g., hematologic abnormality that requires transfusion or hematological stem cell support), or require changes in study medication(s).

Adverse events that begin or worsen after informed consent should be recorded in the Adverse Events CRF. Conditions that were already present at the time of informed consent should be recorded in the Medical History page of the patient's CRF. Adverse event monitoring should be continued for at least 150 days following the last dose of study treatment. After initiation of new post-treatment antineoplastic therapy, only AEs suspected to be related to study treatment will be collected in the Adverse Events CRF. Adverse events (including lab abnormalities that constitute AEs) should be described using a diagnosis whenever possible, rather than individual underlying signs and symptoms. When a clear diagnosis cannot be identified, each sign or symptom should be reported as a separate Adverse Event.

Adverse events will be assessed according to the Common Terminology Criteria for Adverse Events (CTCAE) version 4.03. If CTCAE grading does not exist for an adverse event, the severity of mild, moderate, severe, and life-threatening, corresponding to Grades 1 - 4, will be used. CTCAE Grade 5 (death) will not be used in this study but is collected as a seriousness criterion; information about deaths will be collected through a Death form.

The occurrence of adverse events should be sought by non-directive questioning of the patient (subject) during the screening process after signing informed consent and at each visit during the study. Adverse events also may be detected when they are volunteered by the patient (subject) during the screening process or between visits, or through physical examination, laboratory test, or other assessments. As far as possible, each adverse event should be evaluated to determine:

1. The severity grade (CTCAE Grade 1-4)
2. Its duration (Start and end dates)

3. Its relationship to the study treatment (Reasonable possibility that AE is related: No, Yes)
4. Action taken with respect to study or investigational treatment (none, dose adjusted, temporarily interrupted, permanently discontinued, unknown, not applicable)
5. Whether medication or therapy was given (no concomitant medication/non-drug therapy, concomitant medication/non-drug therapy)
6. Outcome (not recovered/not resolved, recovered/resolved, recovering/resolving, recovered/resolved with sequelae, fatal, unknown)
7. Whether it is serious, where a serious adverse event (SAE) is defined as in [Section 8.2.1](#) and which seriousness criteria have been met

All adverse events should be treated appropriately. If a concomitant medication or non-drug therapy is given, this action should be recorded on the Adverse Event CRF.

Once an adverse event is detected, it should be followed until its resolution or until it is judged to be permanent, and assessment should be made at each visit (or more frequently, if necessary) of any changes in severity, the suspected relationship to the study treatment, the interventions required to treat it, and the outcome.

Progression of malignancy (including fatal outcomes), if documented by use of appropriate method (for example, as per irRC or as per RECIST), should not be reported as a serious adverse event.

Adverse events separate from the progression of malignancy (example, deep vein thrombosis at the time of progression or hemoptysis concurrent with finding of disease progression) will be reported as per usual guidelines used for such events with proper attribution regarding relatedness to the drug.

## **8.1.2 Laboratory test abnormalities**

### **8.1.2.1 Definitions and reporting**

Laboratory abnormalities that constitute an Adverse event in their own right (are considered clinically significant, induce clinical signs or symptoms, require concomitant therapy or require changes in study treatment), should be recorded on the Adverse Events CRF. Whenever possible, a diagnosis, rather than a symptom should be provided (e.g. anemia instead of low hemoglobin). Laboratory abnormalities that meet the criteria for Adverse Events should be followed until they have returned to normal or an adequate explanation of the abnormality is found. When an abnormal laboratory or test result corresponds to a sign/symptom of an already reported adverse event, it is not necessary to separately record the lab/test result as an additional event.

Laboratory abnormalities, that do not meet the definition of an adverse event, should not be reported as adverse events. A Grade 3 or 4 event (severe) as per CTCAE does not automatically indicate a SAE unless it meets the definition of serious as defined below and/or as per investigator's discretion. A dose hold or medication for the lab abnormality may be required by the protocol in which case the lab abnormality would still, by definition, be an adverse event and must be reported as such.

## 8.2 Serious adverse events

### 8.2.1 Definitions

Serious adverse event (SAE) is defined as one of the following:

- Is fatal or life-threatening
- Results in persistent or significant disability/incapacity
- Constitutes a congenital anomaly/birth defect
- Is medically significant, i.e., defined as an event that jeopardizes the patient or may require medical or surgical intervention to prevent one of the outcomes listed above
- Requires inpatient hospitalization or prolongation of existing hospitalization,
- Note that hospitalizations for the following reasons should not be reported as serious adverse events:
  - Routine treatment or monitoring of the studied indication, not associated with any deterioration in condition
  - Elective or pre-planned treatment for a pre-existing condition that is unrelated to the indication under study and has not worsened since signing the informed consent
  - Social reasons and respite care in the absence of any deterioration in the patient's general condition
- Note that treatment on an emergency outpatient basis that does not result in hospital admission and involves an event not fulfilling any of the definitions of a SAE given above is not a serious adverse event.

Progression of underlying malignancy is not reported as an adverse event if it is clearly consistent with the suspected progression of the underlying cancer as defined by RECIST or irRC. Hospitalization due solely to the progression of underlying malignancy should NOT be reported as a serious adverse event.

Clinical symptoms of progression may be reported as adverse events if the symptom cannot be determined as exclusively due to the progression of the underlying malignancy, or does not fit the expected pattern of progression for the disease under study.

Symptomatic deterioration may occur in some patients. In this situation, progression is evident in the patient's clinical symptoms, but is not supported by the tumor measurements. Or, the disease progression is so evident that the investigator may elect not to perform further disease assessments. In such cases, the determination of clinical progression is based on symptomatic deterioration. These determinations should be a rare exception as every effort should be made to document the objective progression of underlying malignancy.

If there is any uncertainty about an adverse event being due only to the disease under study, it should be reported as an AE or SAE.

### 8.2.2 Reporting

For patients with unknown molecular status and who sign the molecular pre-screening ICF, SAE collection will start upon signing the molecular pre-screening ICF. SAEs will only be reported if the event is suspected to be causally related to a study procedure as assessed by the

investigator (e.g. an invasive procedure such as biopsy). SAEs will be followed until resolution or until clinically relevant improvement or stabilization. If the main ICF is not signed (molecular pre-screen failure), SAE collection ends 30 days after the last study related procedure.

For patients who sign the main study ICF, SAE collection starts at time of main study informed consent whether the patient is a screen failure or not. SAEs will be followed until resolution or until clinically relevant improvement or stabilization.

To ensure patient safety, every SAE, regardless of suspected causality, occurring after the patient has provided informed consent and until at least 150 days after the patient has stopped study treatment must be reported to Novartis within 24 hours of learning of its occurrence. If a patient starts a post-treatment antineoplastic therapy, then only SAEs suspected to be related to study treatment will be reported to Novartis.

Any additional information for the SAE including complications, progression of the initial SAE, and recurrent episodes must be reported as follow-up to the original episode within 24 hours of the investigator receiving the follow-up information. An SAE occurring at a different time interval or otherwise considered completely unrelated to a previously reported one should be reported separately as a new event.

Any SAEs experienced after this 150 days period should only be reported to Novartis if the investigator suspects a causal relationship to the study treatment. Recurrent episodes, complications, or progression of the initial SAE must be reported as follow-up to the original episode within 24 hours of the investigator receiving the follow-up information. An SAE occurring at a different time interval or otherwise considered completely unrelated to a previously reported one should be reported separately as a new event.

Information about all SAEs is collected and recorded on the Serious Adverse Event Report Form; all applicable sections of the form must be completed in order to provide a clinically thorough report. The investigator must assess and record the relationship of each SAE to each specific study treatment (if there is more than one study treatment), complete the SAE Report Form in English [**For Japan only: complete the SAE report form in English or Japanese**], and submit the completed form within 24 hours to Novartis. Detailed instructions regarding the submission process and requirements for signatures are to be found in the investigator folder provided to each site.

Follow-up information is submitted in the same way as the original SAE Report. Each re-occurrence, complication, or progression of the original event should be reported as a follow-up to that event regardless of when it occurs. The follow-up information should describe whether the event has resolved or continues, if and how it was treated, whether the blind was broken or not, and whether the patient continued or withdrew from study participation.

If the SAE is not previously documented in the Investigator's Brochure or Package Insert (new occurrence) and is thought to be related to the Novartis study treatment, an oncology Novartis Chief Medical Office and Patient Safety (CMO & PS) department associate may urgently require further information from the investigator for Health Authority reporting. Novartis may need to issue an Investigator Notification (IN), to inform all investigators involved in any study with the same drug that this SAE has been reported. Suspected Unexpected Serious Adverse

Reactions (SUSARs) will be collected and reported to the competent authorities and relevant ethics committees in accordance with Directive 2001/20/EC or as per national regulatory requirements in participating countries.

### **8.3 Pregnancies**

To ensure patient safety, each pregnancy occurring while the patient is on study treatment must be reported to Novartis within 24 hours of learning of its occurrence. The pregnancy should be followed up to determine outcome, including spontaneous or voluntary termination, details of the birth, and the presence or absence of any birth defects, congenital abnormalities, or maternal and/or newborn complications. After the mother has provided consent, the newborn will be followed-up for 12 months.

Pregnancy should be recorded on a Clinical Trial Pregnancy Form and reported by the investigator to the oncology Novartis Chief Medical Office and Patient Safety (CMO & PS). Pregnancy follow-up should be recorded on the same form and should include an assessment of the possible relationship to the investigational treatment and any pregnancy outcome. Any SAE experienced during pregnancy must be reported on the SAE Report Form.

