### **Amendment 05 (30-Sep-2016)**

#### **Amendment rationale**

The protocol is amended to increase the duration of contraception and safety follow-up periods post PDR001 treatment from 90 days to 150 days, using five times the upper limit of the half-life of 23 days and an added safety margin. These changes are related to an Urgent Safety Measure communicated on 08-Jun-2016 to all investigators.

[REDACTED]

[REDACTED]

Therefore, after the start of a new antineoplastic therapy during the safety follow-up, only AEs and SAEs suspected to be related to PDR001 will be collected in order to focus on the collection of information relevant to PDR001; and concomitant medications will be recorded until the 30-day safety follow-up or the start of new antineoplastic, whatever occurred first.

Language relating to bone scans and other radiologic exams for evaluation of bone metastases is clarified.

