22. Use of hematopoietic colony-stimulating growth factors (e.g. G-CSF, GM-CSF, M-CSF)  $\leq$  2 weeks prior start of study drug. An erythroid stimulating agent is allowed as long as it was initiated at least 2 weeks prior to the first dose of study treatment.
23. Pregnant or lactating women, where pregnancy is defined as the state of a female after conception and until the termination of gestation, confirmed by a positive hCG laboratory test.
24. Women of child-bearing potential, defined as all women physiologically capable of becoming pregnant, unless they are using highly effective methods of contraception during dosing and for 150 days after the last dose of PDR001. Highly effective contraception methods include:
  - Total abstinence (when this is in line with the preferred and usual lifestyle of the patient. Periodic abstinence (e.g., calendar, ovulation, symptothermal, post-ovulation methods) and withdrawal are not acceptable methods of contraception
  - Female sterilization (have had surgical bilateral oophorectomy with or without hysterectomy), total hysterectomy or tubal ligation at least six weeks before taking study treatment. In case of oophorectomy alone, only when the reproductive status of the woman has been confirmed by follow up hormone level assessment
  - Male sterilization (at least 6 months prior to screening). For female patients on the study the vasectomized male partner should be the sole partner for that patient.
  - Use of oral, injected or implanted hormonal methods of contraception or placement of an intrauterine device (IUD) or intrauterine system (IUS), or other forms of hormonal contraception that have comparable efficacy (failure rate  $<1\%$ ), for example hormone vaginal ring or transdermal hormone contraception.

In case of use of oral contraception women should have been stable on the same pill for a minimum of 3 months before taking study treatment.

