#### 7.2.2.5.7 Pregnancy and assessments of fertility

Pregnancy tests will be performed for women of child bearing potential.

At screening, a serum pregnancy test must be performed within 3 days before the first dose. During the study (Day 1 of each cycle starting with Cycle 2) a serum or urine pregnancy test must be performed. At End of Treatment, a serum pregnancy test must be performed. A urine pregnancy test should be performed every month during and at the end of the safety follow-up period (i.e. 5 months after the last dose of PDR001). If the patient is not coming to the clinic during the safety follow-up, it can be performed at home or at a local doctor's office, and the results will be communicated to the site staff. These follow-up pregnancy tests will be recorded only in the source documentation, not in the CRF.

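### Section 8.3 sets no explicit pregnancy-reporting window after treatment ends, although contraception, pregnancy testing and SAE reporting run to 150 days after the last dose

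*Protocol*

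**What the plan says.** Protocol Section 8.3 states that "each pregnancy occurring while the patient is on study treatment must be reported to Novartis within 24 hours of learning of its occurrence". The next sentence continues: "The pregnancy should be followed up to determine outcome, including spontaneous or voluntary termination, details of the birth", and the paragraph ends with 12-month follow-up of the newborn, subject to the mother's consent. The second paragraph gives the route, "Pregnancy should be recorded on a Clinical Trial Pregnancy Form and reported by the investigator", and carries no time limit of its own.

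Three other rules use a longer window.

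- Section 5.3, criterion 24, excludes women of child-bearing potential "unless they are using highly effective methods of contraception during dosing and for 150 days after the last dose of PDR001".
- Section 7.2.2.5.7 says "A urine pregnancy test should be performed every month during and at the end of the safety follow-up period", and places the end of that period five months after the last dose. Table 7-1 footnote 4 agrees. On recording, Section 7.2.2.5.7 adds: "These follow-up pregnancy tests will be recorded only in the source documentation, not in the CRF".
- Section 8.2.2 requires every SAE to be reported, whatever its suspected cause, until at least 150 days after treatment stops. It narrows to SAEs suspected to be related once a new antineoplastic therapy starts, and again after day 150.

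The Amendment 05 rationale gives the basis of the 150 days as "using five times the upper limit of the half-life of 23 days and an added safety margin". The SAP has no rule on pregnancy reporting.

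**The concern.** The protocol looks for pregnancy every month after the last dose, but the rule that makes a pregnancy reportable is worded for the treatment period only. Read literally, a woman who conceives in the second month after her last dose would have a positive protocol test, and nothing would expressly tell the site to send a pregnancy form or to follow the outcome and the newborn. Section 7.2.2.5.7 says where the test result is filed but not what a positive result sets in motion.

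At stake is the completeness and consistency of the safety record for a first-in-human antibody. A site that reads 8.3 narrowly and one that reads it broadly would handle the same event differently, each with support in the text.

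**Working it through.** No sample size, power or error rate is involved, so the check compares windows and traces which rule catches which event.

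**1. Length of the gap.** Inputs: the 150-day post-dose window (Sections 5.3, 7.2.2.5.7, 8.2.2 and Table 7-1 footnote 4), and the post-dose days that 8.3 names, which is 0.

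- Literal reading: 150 − 0 = 150 days, holding about five monthly tests.
- 8.3 does not define being on study treatment. If the on-treatment analysis period of Protocol Section 10.5.3.1 is borrowed (to 30 days after the last dose): 150 − 30 = 120 days.
- If the SAP's last date of exposure is borrowed (SAP Section 3.2.1.3: last dose plus 13, 20 or 27 days for Q2W, Q3W or Q4W): 137, 130 or 123 days.

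On every reading at least 120 of the 150 days remain outside the explicit rule.

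**2. Basis of the 150 days.** 5 × 23 = 115 days, leaving an implied margin of 150 − 115 = 35 days. The margin is not stated, so 150 cannot be reproduced exactly; nothing below depends on it.

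**3. Is exposure plausible inside the gap?** Assume simple first-order decay from the level at the start of the period.

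- Half-life 23 days (upper limit, Amendment 05): 0.5^(30/23) = 0.40 at day 30 and 0.5^(150/23) = 0.011 at day 150.
- Half-life 10 to 20 days (expected range, Section 2.3): 0.5^(30/10) = 0.125 to 0.5^(30/20) = 0.35 at day 30.

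So 12.5% to 40% remains at day 30, where even the 30-day reading of the trigger ends. This is context only; the mismatch of windows stands without it.

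**4. Which rule catches which event.**

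| Event | Explicit rule |
|---|---|
| Conceived on treatment, whenever detected | 8.3: 24-hour report, outcome and newborn follow-up |
| Conceived after treatment, within 150 days, uncomplicated | None |
| Same, serious complication by day 150, no new antineoplastic therapy | 8.2.2: SAE, regardless of causality |
| Same, after new antineoplastic therapy starts | 8.2.2: SAE only if suspected related |
| Same, birth defect found after day 150 | 8.2.1 and 8.2.2: SAE only if suspected related |

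The last row is the usual case for a birth defect. Taking about nine months from conception to birth (an assumption), a birth following conception in the window falls beyond day 150. Pregnancy itself is not an SAE criterion in 8.2.1.

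**5. Does another section close the gap?** Section 7.1.6 lists the CRFs for data collected in follow-up, and the Clinical Trial Pregnancy Form is not among them. Appendix 14.1.4.3 lists pregnancy as a possible reason for completing the post-treatment phase, but a positive test does not oblige a site to use it. No section extends the 8.3 trigger.

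**The case against.** The strongest reply is that 8.3 can be read more widely than its first sentence. Its second paragraph has no time limit, and its closing sentence sends any SAE during pregnancy to the SAE form, again without one. A site holding a positive month-2 test could reasonably complete the form. This stands in part: the text permits that reading but does not require it, because the paragraph follows and depends on a sentence limited to treatment. It shows ambiguity rather than coverage.

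A reader might also infer three stronger conclusions, which the documents do not support.

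- *No positive follow-up test triggers a report.* The trigger turns on when the pregnancy occurs, so one conceived on treatment and detected later is still reportable within 24 hours. Filing test results in source does not block a report either, because pregnancies go on a separate form and home or local results are communicated to site staff.
- *The sponsor would never learn of such a pregnancy, or no CRF entry could arise.* Serious complications have the SAE route, monitors have access to source documents (Section 9.2), and the disposition page can record pregnancy. None of these requires a pregnancy report or outcome follow-up, but they rule out the absolute claim.
- *The CSR would under-report pregnancies.* Neither document specifies a pregnancy table or listing, on or off treatment, and Section 10.5.3.2 lists all AEs and SAEs including post-treatment ones.

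Finally, few patients may be affected. Enrollment closed on 22-Mar-2018, 25 patients were on treatment on 06-May-2019, patients who transfer to another study or treatment option skip the 150-day follow-up (Section 7.1.6), and highly effective contraception is required throughout the window. That limits the severity but leaves the mismatch, and earlier patients' follow-up is not excluded from the concern.

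**Conclusion.** The point holds as a mismatch between safety-reporting windows. For a pregnancy conceived after treatment ends but within 150 days of the last dose, the protocol gives no explicit requirement to report it, follow its outcome or follow the newborn. The gap is 150 days on the literal wording and 120 on the widest reading considered. SAE reporting fills it only for serious events, and only for those suspected related once new antineoplastic therapy has started or day 150 has passed.

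This is a low-frequency alignment issue, worth correcting but not critical. No endpoint, dose decision or planned analysis rests on it. The number of women of child-bearing potential is not given, so expected events cannot be estimated. The conclusion rests on reading the second paragraph of 8.3 as dependent on the first; if the sponsor intended the broad reading, the same edit would simply say so.

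**What to change.** In Section 8.3, extend the reporting trigger to pregnancies occurring on study treatment or within 150 days after the last dose of PDR001, so that it matches the window already used in Sections 5.3, 7.2.2.5.7 and 8.2.2. Outcome and newborn follow-up then apply to the same pregnancies without further change.

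In Section 7.2.2.5.7 and Table 7-1 footnote 4, add that a positive follow-up test is reported on the Clinical Trial Pregnancy Form under 8.3. Negative tests can stay in source documents.

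For follow-up already completed, check source records for positive tests before the final CSR and obtain a form and outcome where one is found.

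The protocol cost is one phrase in 8.3 and one sentence in each of the other two places. The tests and the form already exist, so the ongoing burden is the occasional positive result. The source check is a one-off task limited to women of child-bearing potential who entered safety follow-up. No dose, schedule or clinical management rule changes.
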